The majority of women entered the study reporting elevated depressive symptoms and experienced a significant decline in depressive symptoms in the follow-up period, a finding that has been observed in other populations (22, 23). These results are encouraging, as recent trajectory analyses from our group show that without intervention, disturbed sleep and depressive symptoms are relatively stable or increasing in the perinatal period (24, 25). Further, results from a systematic review and meta-analysis currently being conducted in our lab, which includes over 4,000 subjects, suggests that on average sleep quality declines significantly from early to late pregnancy; in contrast, group treatment with 5-sessions of CBT-I significantly improved sleep quality, even as pregnancy progressed.

Objectives

The primary aim of the current project is to evaluate the impact of a 6-week in-person CBT-I versus iCBT-I versus a waitlist (WL) in reducing symptoms of insomnia (assessed subjectively by self-report and objectively with actigraphy) experienced in pregnancy. We hypothesize that

participants who receive a 6-week program CBT-I and iCBT-I (versus WL) will report fewer insomnia symptoms and have improved objectively assessed sleep as measured by at one-week (T2) post treatment. Based on previous research findings, we do not expect that there will be a difference between in-person CBT-I and iCBT-I administration.

The secondary aim is to investigate if CBT-I versus WL reduces symptoms of depression at T2 (one week post-treatment). We hypothesize that participants who receive CBT-I and iCBT-I (versus WL) will report fewer depressive symptoms as measured at T2.

METHODS

Trial Design

The proposed study is a randomized controlled trial of the efficacy of CBT-I for the treatment of insomnia experienced during pregnancy compared to WL. Assessments will occur at baseline, between 12-30 weeks of pregnancy (T1), and at one week posttreatment (T2).

Recruitment Strategy

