Participants will be randomly allocated to in-person CBT-I or iCBT-I or WL. Randomization will be determined using an online research randomization tool (27), which is not predictable and eliminates potential experimenter bias (28). Forty-five participants will be enrolled in the pilot RCT, with 15 randomized into each study group. A staff member who is not associated with the study will conduct the randomization and sequence generation and will put each participant assignment into opaque envelopes that contain the results of the randomization. After a baseline assessment is completed a study therapist will open an envelope and inform participants of their assignment.

Participants randomized to in-person or online treatment will be invited to participate in 6 sessions of CBT-I. Participants randomized to the waitlist group, will receive a pamphlet with information about community resources for pregnant women.

Week 2- Week 7: If randomized to the in-person treatment group, participants will be invited to attend 6 in-person sessions of cognitive-behavioural therapy for insomnia, which will take place at the University of Calgary in a newly renovated research space (*see Appendix A for the structure of each session*). Additionally, they will receive a manual which will include weekly readings relevant to the material being taught in the sessions and an informational pamphlet with helpful community resources for pregnant women. During this intervention, they will become familiarized with self-management approach for insomnia, sleep basics and sleep restriction, stimulus control, problem solving to cope with sleep disturbances and relapse prevention.

Participants randomized to online cognitive behavioural treatment (iCBT-I) will complete a series of 6 modules, where the main learning components are included in video and audio materials. To log onto the CBT-I intervention website, participants will be given login information through an anonymized email address, which will be used only for the duration of the study. Like the in-person intervention, the iCBT-I intervention includes instruction and homework on sleep hygiene and relaxation strategies. Participants will be contacted regularly by a member of the study team to ensure that there are no issues with accessing online readings and audio/visual materials (29).

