Participants in the waitlist group will receive regular obstetric care provided according to the needs and current regime of the patient. The amount of contact with health care professionals outside of the study will be reported, as well as any treatment for insomnia (e.g., medication use) that the control participant engages in.

Week 8 (T2): After 8 weeks, all the participants will be invited to complete the same set of questionnaires from the baseline assessment. Additionally, they will be provided with an actiwatch and asked to wear it for seven days during weekdays. WL participants will be offered the opportunity to access the iCBT-I treatment.

3-Months Postpartum (T3): At 3-months postpartum, all participants will be invited to a web-link with the same set of questionnaires from the previous points of assessment, as well as one additional questionnaire assessing infant sleep quality. The web-linked questionnaires are expected to take approximately 30 minutes to complete.

Equipment

Participants will be provided with an actigraphy device (Actiwatch II, Phillips, USA) and asked to wear it for 7 consecutive days at each assessment point.

Outcome Measures

Complete descriptions of outcome measures are provided in Table 1.

Primary Outcome Measures

Insomnia Interview Schedule (IIS), Insomnia diagnosis will be confirmed using the IIS, which produces reliable and valid insomnia diagnoses, and provides information about developmental course and impact (21).

Insomnia Severity Index (ISI) (21, 30, 31). The ISI is a 7-item questionnaire designed to identify cases of insomnia and evaluate treatment outcomes. The ISI assesses severity of sleep onset, sleep maintenance and early wakening problems, sleep dissatisfaction and perceived distress caused by sleep problems and it was found to be a clinically useful tool in assessing changes in insomnia symptoms in insomnia treatment research (31).

Pittsburgh Sleep Quality Index (PSQI). The PSQI instrument is used in assessing one's sleep quality during the previous month. It consists of 19 self-rated items and 5 questions rated by the roommate or bed partner. There are seven components of the PSQI and these are subjective sleep quality, sleep latency, sleep duration, habitual sleep efficiency, sleep disturbances, use of sleeping medications and daytime dysfunction. A score higher than 5 suggests poor sleep quality (32).

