For assessing sleep quantity and quality, actigraphy (Actiwatch II, Phillips, USA) and sleep daily logs will be used in this study. Actigraphy monitoring provides objective information on circadian rhythm amplitude, acrophase, and mesor as well as indices of sleep efficiency, sleep latency, total sleep time, and number and frequency of awakenings (33). Participants will be asked to wear the actigraph for a period of 7 days at each assessment point.

Secondary Outcome Measures

Edinburgh Postpartum Depression Scale (EPDS) (34). Symptoms of depression in pregnancy and the postpartum will be assessed by the EPDS. The EPDS consists of 10 items and is a reliable and valid tool for identifying symptoms of depression experienced in pregnancy and the postpartum (35).

Additional Measures and Questionnaires

Additional questionnaires include the Multidimensional Fatigue Symptom Inventory-Short Form (MFSI-SF) (36), Dysfunctional Beliefs and Attitudes about Sleep Questionnaire (DBAS-16) (37), Sleep Self-Efficacy Scale (SES) (38), Sleep Hygiene Index (39), Pre-Sleep Arousal Scale (40), Glasgow Sleep Effort Scale (41), Sleep-Related Behaviors Questionnaire (SBRQ) (42), Epworth Sleepiness Scale (ESS) (43), Edinburgh Postnatal

Depression Scale (EPDS) (88), Generalized Anxiety Disorder (GAD-7) (44), Couple Satisfaction Index (CSI-16) (45), the Big Five Inventory (BFI-44) (46), the Extended Brief Infant Sleep Questionnaire (BISQ) (47), the Pregnancy-Specific Anxiety Measure (48), the PROMIS Adult Version 1.0 Pain Interference Short Form 8a (49), and the PROMIS Adult Version 1.0 Pain Intensity Short Form 3a (49).

Data will also be collected regarding demographic and psychosocial variables known to impact sleep. Demographic information collected will include age, family socioeconomic status, and number of children at home. Health practices assessed include smoking, alcohol consumption, and level of habitual exercise. Assessment of previous mental health problems, sleep disorders and psychotropic medication use will be assessed via interview.

ANALYSIS PLAN

Sample Size Power Calculation

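### The plan's sections disagree on which outcomes are primary, and Hypothesis 1 does not say how the two active arms are to be tested against waitlist

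*Combined protocol and SAP*

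**What the plan says.** The plan ranks its outcomes in three places.

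- **Objectives.** The primary aim concerns "reducing symptoms of insomnia (assessed subjectively by self-report and objectively with actigraphy) experienced in pregnancy", and its hypothesis is that treated participants "will report fewer insomnia symptoms and have improved objectively assessed sleep". The other aim is separate: "The secondary aim is to investigate if CBT-I versus WL reduces symptoms of depression at T2".
- **Primary and Secondary Outcome Measures.** Besides the ISI, the primary heading covers the IIS ("Insomnia diagnosis will be confirmed using the IIS, which produces reliable and valid insomnia diagnoses"), the PSQI ("The PSQI instrument is used in assessing one's sleep quality during the previous month") and objective and diary sleep ("For assessing sleep quantity and quality, actigraphy (Actiwatch II, Phillips, USA) and sleep daily logs will be used in this study"). The secondary heading covers only depression: "Symptoms of depression in pregnancy and the postpartum will be assessed by the EPDS".
- **Analysis Plan.** Sample Size Power Calculation names one primary response variable, ISI change from baseline to post-treatment, although it labels both time points T2. Hypothesis 1 is worded on the ISI alone. Secondary Aims holds IIS diagnosis (Hypothesis 2.2) and actigraphy (Hypothesis 2.3). No hypothesis names the PSQI or the sleep logs.

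On the arms, Procedures states "Forty-five participants will be enrolled in the pilot RCT, with 15 randomized into each study group". Hypothesis 1 compares in-person and online CBT-I with waitlist (WL). The sample size text adds that both formats are expected to do better than WL. Neither passage says whether the active arms are pooled or tested separately, or whether one or both must succeed. Sample Size Power Calculation names repeated-measures ANOVA for the primary response; Primary Aims names generalized estimating equations (GEE).

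**The concern.** IIS diagnosis and actigraphy are each primary in one section and secondary in another. The PSQI and sleep logs are labelled primary but have no hypothesis behind them. If the ISI result were unclear and actigraphy or the PSQI looked favourable, an author could cite the Objectives or the outcome list and report that result as primary. A reader could not show from the protocol that this was wrong.

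The arm question matters for a similar reason. With two active arms and one control, pooling, requiring both arms to win and accepting either arm are different tests. They differ in false-positive rate, in power and in the claim that they support. The plan states an alpha, a power and directional hypotheses, so being a pilot of 45 does not remove the need to choose.

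**Working it through.** **1. Labels side by side.**

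| Measure | Objectives | Outcome list | Analysis plan |
|---|---|---|---|
| ISI | primary, as self-report (not named) | primary | primary, Hypothesis 1 |
| Actigraphy | primary | primary | secondary, Hypothesis 2.3 |
| IIS diagnosis | not named | primary | secondary, Hypothesis 2.2 |
| PSQI | at most implied by self-report | primary | absent |
| Sleep logs | at most implied by self-report | primary | absent |
| EPDS | secondary, as depression (not named) | secondary | secondary, Hypothesis 2.1 |

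Only the ISI and the depression scale keep one rank throughout.

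**2. Exposure if the outcome list is read literally.** Five measures, each tested two-sided at 0.05, with any one counting and no true effect:

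- Independent: 1 − (1 − 0.05)^5 = 1 − 0.774 = 22.6%.
- Equal correlation of 0.7 between test statistics (assumed; simulated): about 15%.
- ISI alone: 5%.

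**3. The plan's own sample size figure.** The plan states 18 patients for 95% power at d = 0.8. A two-group t test needs 41 per arm for that, and 18 per arm gives 0.645. Eighteen is reached, for example, as a total in a three-group, two-time repeated-measures ANOVA with an assumed correlation near 0.7. That is an overall test of the three arms, not of any rule below. The derivation of 18 is a separate question and does not affect this point.

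**4. Error and power by rule.** The assumptions are normally distributed ISI change, d on the change scale, equal effects in both active arms, t tests at two-sided 0.05 and complete data. The plan states 14 per group. Twelve per arm is 15 × (1 − 0.20), an assumed completer count.

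- Pooled, noncentrality d / √(1/n + 1/(2n)). At n = 14: 0.8 / √(1/14 + 1/28) = 2.44 on 40 df, power 0.66. At n = 12: 0.8 / √(1/12 + 1/24) = 2.26 on 34 df, power 0.59.
- One active arm against WL, noncentrality d / √(2/n). At n = 14: 2.12 on 26 df, power 0.53. At n = 12: 1.96 on 22 df, power 0.47.
- The two single-arm contrasts share the WL arm, so the joint rules were simulated (300,000 runs).

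| Rule | Error, no effect | Power d = 0.8, n = 14 / 12 | Power d = 1.1, n = 14 / 12 |
|---|---|---|---|
| Both arms must win | 0.9% | 0.37 / 0.30 | 0.69 / 0.60 |
| Pooled active vs WL | 5.0% | 0.66 / 0.59 | 0.91 / 0.86 |
| Either arm, unadjusted | 9.1% | 0.70 / 0.63 | 0.91 / 0.87 |

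The errors count significance in either direction. By symmetry, about half of each falls in favour of treatment.

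If d = 0.8 refers to T2 scores and change is analysed, d on change is 0.8 / √(2(1 − r)). That is 0.68, 0.80 or 1.03 at r = 0.3, 0.5 or 0.7 (assumed). At 12 per arm, power then runs from 0.20 to 0.53 (both) and from 0.46 to 0.81 (pooled).

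**5. The primary model.** No variance estimator is named for the GEE. Suppose an uncorrected sandwich Wald test with a normal reference (an assumption). The pooled statistic is [(mean A + mean B)/2 − mean WL] / √[(s²A + s²B)/(4n) + s²WL/n], with each s² using divisor n. Its null error is 7.4% at n = 12 and 6.9% at n = 14. With the Mancl-DeRouen variance and t on 36 − 3 = 33 df, it is 4.5% at n = 12.

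**The case against.** The strongest reply is that the section governing the analysis is clear. The primary response variable, the power statement and Hypothesis 1 all point to the ISI, so a careful reader knows which test is primary. That stands, and it is why the defect is repairable rather than fatal. It does not remove the contradiction, because the Objectives and the outcome list carry equal authority in one document.

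Other points partly stand:

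- The IIS is also the eligibility tool, which may explain its place under the primary heading. Hypothesis 2.2 still makes it a secondary outcome.
- The Objectives join self-report and objective sleep with an *and*. If that means that both must succeed, error falls rather than rises: 0.3-2.9% for the pooled test with one actigraphy measure (correlation 0 to 0.9 assumed). The 15-23% applies only to an any-measure reading, which no section states.
- Labelling baseline as T2 is an evident slip, since Trial Design defines it as T1. Under randomisation, ISI change and ISI at T2 address the same between-arm effect, with different precision.

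A reader might infer three stronger things that the documents do not support:

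- **That Hypothesis 1 states no comparison.** It gives comparator, direction, outcome and time. Only the pooled-or-separate choice and the success rule are missing.
- **That the planned test runs at 9% error.** This needs the either-arm reading, which the wording supports least.
- **That requiring both arms still exceeds 5% when one arm works and the other does not.** With d = 1.6 in one arm, none in the other and 12 per arm, the second arm is significant in some direction along with the first in 4.6% of runs (t tests) or 6.9% (uncorrected sandwich). These counts include runs where the ineffective arm is worse than WL. Hypothesis 1 is directional; counting only wins over WL gives 2.5% and 3.7%.

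**Conclusion.** The concern holds in a limited form and should be fixed. The outcome hierarchy contradicts itself across the Objectives, the outcome list and the analysis plan; this rests on the text alone. The 15-23% figure measures what the loose labels would permit, not what the plan intends.

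The missing success rule is a real but smaller gap. Both readings that the text supports hold 5% with t tests. What stays open is power (0.37 or 0.66 at d = 0.8 and 14 per arm) and the scope of the claim. Neither reading is clearly the intended one: the stated expectation for both formats favours separate tests, while the secondary aim, worded as CBT-I against WL, favours pooling. The excess error of about 7% under GEE depends on an assumed uncorrected variance estimator.

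**What to change.** 1. **Outcome labels.** In the Objectives and the outcome list, make ISI change from T1 to T2 the only primary outcome. Move IIS diagnosis and actigraphy to the secondary place that they already have in Secondary Aims. List the PSQI and sleep logs as secondary or additional measures; the hypotheses do not mention them, so their role has to be written in. Correct the baseline label to T1 in Sample Size Power Calculation.
2. **One rule for Hypothesis 1, fixed before any by-arm look at T2 data.** Either each active arm is tested against WL at two-sided 0.05 and both must win, or one pooled contrast is tested with the claim limited to CBT-I averaged over formats. The choice is the sponsor's. State the power of the chosen rule, and whether d refers to change or to T2 scores.
3. **One primary model.** Choose repeated-measures ANOVA or GEE. If GEE, specify a small-sample variance correction, such as Mancl-DeRouen, with a t reference.

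**Cost.** No extra participants or visits are needed. The stated power falls below that of an unadjusted either-arm reading: 0.70 at 14 per arm and d = 0.8, against 0.66 pooled or 0.37 with both required. The pooled rule cannot support a claim for each format. If only one arm works (d = 0.8, 12 per arm), it is still significant in 17-20% of trials, depending on how the variance is estimated.

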The primary response variable, change in symptoms on the Insomnia Severity Index (ISI) between baseline (T2) and post treatment follow-up (T2), will be analyzed with using Repeated Measures Analysis of Variance (ANOVA) with a linear distribution specified at a significance level of $\alpha = 0.05$. Using data from our pilot study, and insomnia symptoms on the ISI, we found that pre-post treatment yielded a $d = 3.07$. Prior studies of CBT-I for patients with insomnia have found large between-group effect sizes in a range from $d = 1.1$ to $d = 1.6$, even in patients with comorbid mental illness; however, we completed our power calculations using a more conservative effect size estimate, which showed that 18 patients are required to have a 95% chance of detecting a between-group effect size of $d = 0.8$ at a significance level of $\alpha = 0.05$ on the ISI. Although we had no attrition from our pilot study, we added a potential attrition rate of 20%, resulting in 14 participants to detect group differences in our pilot RCT.

Based on previous research, we do not expect to see differences in iCBT-I versus in person CBT-I; however, we expect that both conditions will outperform the WL group. Although we had no attrition from our pilot study, we calculated a potential attrition rate of 20% based on previous research in this area, resulting in 45 participants in our pilot RCT. Across 3 arms, this will allow 14 participants in each group and will provide a power of more than 90% to detect a difference of 8 points on the ISI, which is indicative of a clinically significant change (30).

Primary Aims

Hypothesis 1) Participants who receive in-person and online CBT-I (versus WL) will report fewer insomnia symptoms as measured by Insomnia Severity Index (ISI) at the post treatment assessment point (T2).

Primary aims will be assessed using Generalized Estimated Equations (GEE) and an intent-to-treat (ITT) basis, including data for each participant who was randomized, regardless of their

adherence to the intervention or whether they withdraw from the study. Analyses including only patients fulfilling the treatment will also be conducted.

Secondary Aims

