Hypothesis 2.1) Participants who receive in-person and online CBT-I (versus WL) will experience fewer symptoms of depression as assessed by the Edinburgh Postpartum Depression Scale (EPDS) and will be less likely to be diagnosed with depression as assessed using Structured Clinical Interview for the DSM-IV (SCID) at T2.

Hypothesis 2.2) Participants who receive online and in-person CBT-I (versus WL) will be less likely to be diagnosed with insomnia, as measured by the Insomnia Interview Schedule (21), at T2.

Hypothesis 2.3) Participants who receive in-person and online CBT-I (versus WL) will experience better objective sleep as assessed by actigraphy (higher sleep efficiency and lower sleep onset latency) at T2.

Secondary aims including changes in actigraphy parameters, diagnosis of insomnia, symptoms of and diagnoses of depression will be examined. Changes in binary outcomes will be tested using Generalized Estimated Equations (GEE) with a binary outcome specified.

RESEARCH MANAGEMENT

[name], as the Primary Investigator will be responsible for the overall management of the project. She received extensive training in cognitive behavioral interventions and will be responsible for training clinical psychology master's students in the delivery of in-person cognitive behavioural therapy for insomnia adapted for pregnant women. [name] is an experienced clinician and will provide clinical support regarding the establishment of therapy protocols and ongoing consultation regarding fidelity to the CBT treatment protocol. [name] will be responsible for supervising master's students in administering diagnostic interviews for Axis I mood disorders. [name] will be responsible for supervising the research assistant at the University of Manitoba who will be coordinating the online portion of the intervention.

RESEARCH ENVIRONMENT

All assessments and in-person CBT-I sessions will take place at the University of Calgary in a newly renovated research space designed specifically for conducting and evaluating evidence-based interventions which is located in suite 292 of the Education Classroom Building.

REFERENCES

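### No adjustment for baseline ISI is specified in the primary analysis, although ISI is collected at T1; naming it would usually narrow the interval and raise power in arms of 12 to 15 women at almost no cost

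*Combined protocol and SAP*

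**What the plan says.** Under Sample Size Power Calculation the plan defines the endpoint: "The primary response variable, change in symptoms on the Insomnia Severity Index (ISI) between baseline (T2) and post treatment follow-up (T2". Both time points are labelled T2 there. Trial Design makes clear that baseline is T1: "Assessments will occur at baseline, between 12-30 weeks of pregnancy (T1), and at one week posttreatment (T2". The method given for this endpoint is "Repeated Measures Analysis of Variance (ANOVA) with a linear distribution specified at a significance level of" 0.05. No covariate is named.

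Under Primary Aims, Hypothesis 1 is worded as a level and not a change: participants in the CBT-I arms "will report fewer insomnia symptoms as measured by Insomnia Severity Index (ISI) at the post treatment assessment point (T2". The model there is different: "Primary aims will be assessed using Generalized Estimated Equations (GEE) and an intent-to-treat (ITT) basis". Its terms, covariates and working correlation are not given.

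Baseline ISI will be available. In Procedures, at T2, "all the participants will be invited to complete the same set of questionnaires from the baseline assessment". On size, Procedures says "Forty-five participants will be enrolled in the pilot RCT, with 15 randomized into each study group". The power text works with 14 per group, and its 20% attrition applied to 15 leaves 12.

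The Secondary Aims text refers to "Secondary aims including changes in actigraphy parameters" and names a model only for binary outcomes.

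**The concern.** With two time points, the group-by-time test in a repeated measures ANOVA is the test of the arm difference in raw change. Raw change subtracts the whole baseline value, which fixes the coefficient on T1 ISI at 1. If the true slope of T2 on T1 is below 1, this carries avoidable noise. An analysis that estimates the slope targets the same randomised effect with a smaller standard error.

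At stake is precision. In arms of 12 to 15, interval width and power can change materially according to whether baseline ISI enters the model. The plan should settle that before data are seen.

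**Working it through.** **The plan's own figure.** The plan states that 18 patients give 95% power at d = 0.8 and alpha 0.05, without saying per arm or in total. A two-sided two-sample comparison needs 2 × (1.960 + 1.645)² / 0.8² = 40.6, so 41 per arm (42 with the t distribution). At 18 per arm the power is about 65%. The figure does not reproduce as a between-group comparison. That is a separate matter; the rest of the check compares two analyses at the arm sizes planned.

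**Inputs.** From the documents: d = 0.8, alpha 0.05 (two-sided assumed), three equal arms, 15 randomised per arm, 12 after 20% loss. Not in the documents: the T1 SD (s1), the T2 SD (s2) and the T1–T2 correlation r. These are varied below. The 0.8 is taken in units of the T2 SD.

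**Variance per woman.**
- Raw change: s1² + s2² − 2·r·s1·s2
- Baseline-adjusted: s2²(1 − r²)
- Difference: (s1 − r·s2)², which is never negative

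With s1 = s2 the ratio adjusted/change is (1 + r)/2, that is 0.65, 0.75 and 0.85 at r = 0.3, 0.5 and 0.7.

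**One case in full (15 per arm, r = 0.5, SD = 1).**
- Change: variance 1.00, SE = √(2 × 1.00/15) = 0.365, 42 df, 95% half-width 0.737.
- Adjusted: variance 0.75 × (1 + 1/40) = 0.769, where the bracket is the small-sample factor 1 + 1/(3n − 5). SE = √(2 × 0.769/15) = 0.320, 41 df, half-width 0.647.
- The interval is 12% narrower. Noncentral-t power goes from 57% to 68%.

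**Equal SDs, one CBT-I arm versus waitlist, d = 0.8, change → adjusted.**

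| r | 95% CI narrower by | Power, 12 per arm | Power, 15 per arm |
|---|---|---|---|
| 0.3 | about 18% | 36% → 50% | 44% → 60% |
| 0.5 | about 12% | 48% → 58% | 57% → 68% |
| 0.7 | 6–7% | 69% → 75% | 79% → 84% |

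Simulated trials of 14 per arm gave SE ratios of 0.82, 0.88 and 0.93, against 0.81, 0.87 and 0.92 in theory. In simulation, type I error was 4.5–5.4% for both methods.

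**Unequal SDs, 12 per arm, difference 0.8 × T2 SD.**
- s2/s1 = 0.8, r = 0.5: variance ratio 0.48/0.84 = 0.57; power 38% → 58%.
- s2/s1 = 1.25, r = 0.5: 55% → 58%.
- s2/s1 = 1.5: variance ratios 0.87, 0.96 and 1.00 at r = 0.3, 0.5 and 0.7; power 46% → 50%, 58% → 58% and 76% → 75%.

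**The plan's 8-point target, equal SDs.** With SD 5 (assumed) and r = 0.5, change-score power is already 97% at 12 per arm and 99% at 15. At r = 0.3 and 12 per arm it goes from 90% to 98%. With SD 7 and r = 0.5 it goes from 78% to 87% at 12 and from 86% to 94% at 15.

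**What the GEE does.** In a simulated data set, a GEE with group, time and group-by-time returned exactly the change-score estimate (−0.437). A GEE with a common baseline mean gave −0.426, as did ANCOVA. The missing model terms therefore decide the matter.

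**The case against.** The strongest objection is that an unadjusted analysis is being read from silence. The change-score sentence stands in the sample-size text, while Primary Aims words the hypothesis at T2 and names a GEE without terms. This stands in part. A reader might infer that both named models lose precision, but the documents show that only for the repeated measures ANOVA; a GEE with a common baseline mean would not. A reader might also infer that baseline is ignored altogether. It is not: a change score subtracts it, and the loss is only relative to an analysis that estimates the slope.

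The size is open to challenge too, because it rests on SDs and a correlation that the plan does not give. This also stands, and is why a range is shown.

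Two further inferences are tempting and fail. One is that recruiting only women with insomnia enlarges the loss. Selection on baseline lowers r but also lowers the T1 SD and leaves a linear slope unchanged, so it can reduce the gain; entry in any case uses the Insomnia Interview Schedule, with no ISI cutoff stated. The other is that chance baseline imbalance is an additional harm. Its effect averages zero and is already part of the larger change-score variance.

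Finally, plain ANCOVA on T2 drops women without T2 data, which conflicts with the promise to include every randomised participant. That is correct and shapes the fix.

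**Conclusion.** The point holds as one of efficiency and specification. Change in ISI by repeated measures ANOVA is the raw change-score comparison, the GEE is unspecified, and neither is stated to use a baseline value that the trial collects.

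With equal SDs and r between 0.3 and 0.7, adjustment narrows the interval by about 18% down to 6% and adds roughly 5 to 16 points of power at d = 0.8. The gain is larger if the T2 SD is below the T1 SD. If the T2 SD is about 1.5 times the T1 SD it is small or nil, at worst a loss of one to two points. If the true effect is 8 points with SD 5, little power is left to gain at r = 0.5, though the interval still narrows.

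Nothing here shows bias or an inflated type I error. The change is worth making because the likely gain far exceeds the possible loss.

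**What to change.** Name one primary model for ISI and state that it includes baseline ISI. The preferred form is a two-time-point GEE or mixed model with a common baseline mean across arms. This keeps randomised women who lack a T2 value, in line with the intent-to-treat statement. The alternative is T2 ISI with T1 ISI as a covariate, plus a stated method for missing T2 values; using change as the outcome with the same covariate gives the same arm effect. Raw change can stay as a descriptive figure. Correct the baseline label from T2 to T1 in the same edit.

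Use the same form, each with its own baseline value, for EPDS, sleep efficiency and sleep onset latency, for which no model is now named.

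The cost is a few sentences and one model term: no new data, visits or participants. The sample-size statement needs its own correction, since adjustment does not rescue it: at 14 per arm and d = 0.8, with equal SDs, pairwise power reaches 95% only at r between 0.8 and 0.9.

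### The attrition arithmetic behind N = 45 does not close: 18 with 20% loss cannot become 14, and 45 with 20% loss leaves 12 per arm, not the 14 at which power is quoted

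*Combined protocol and SAP*

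**What the plan says.** The Sample Size Power Calculation section of the Analysis Plan contains two linked calculations.

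- The first concerns a between-group effect of d = 0.8 at alpha 0.05: "18 patients are required to have a 95% chance of detecting a between-group effect size" of that size. It continues: "we added a potential attrition rate of 20%, resulting in 14 participants to detect group differences in our pilot RCT". Neither number is labelled as per arm or total.
- The second, in the next paragraph, reads "we calculated a potential attrition rate of 20% based on previous research in this area, resulting in 45 participants in our pilot RCT", and adds, of the three-arm total, that "this will allow 14 participants in each group and will provide a power of more than 90% to detect a difference of 8 points"; these are ISI points.

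The Procedures section fixes enrolment: "Forty-five participants will be enrolled in the pilot RCT, with 15 randomized into each study group".

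The response variable is the change in ISI from baseline to post-treatment. The power section names repeated-measures ANOVA for it, and the Primary Aims section names GEE on an intent-to-treat basis. No ISI standard deviation, within-person correlation or sidedness is given for either calculation.

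**The concern.** An attrition allowance raises the number to recruit above the number needed for analysis. Here it lowers it, from 18 to 14. The same 14 then reappears as the number per group from 45 participants, although 20% loss from 15 per arm does not leave 14.

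This section is the plan's only justification for 45 participants. The number enrolled is clear. Two things are not: how many women are expected to have a T2 score, and what power that number gives. The only power quoted for the planned trial is tied to 14 per arm, which the plan's own allowance does not deliver.

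**Working it through.** **Inputs from the documents.** Required number 18; attrition 20%; 45 enrolled, 15 per arm, three arms; power above 90% quoted at 14 per arm for 8 ISI points; alpha 0.05.

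**Step 1: from 18 to 14.** Number to recruit = number required / (1 − loss).
- 18 / 0.8 = 22.5, so 23.
- The plan's 14 is reproduced only by subtracting the loss: 18 × 0.8 = 14.4. That is fewer than the 18 just called required.
- Suppose the two were transposed, with 14 needed and 18 recruited per arm: 14 / 0.8 = 17.5, so 18. Three arms then need 3 × 18 = 54, not 45.

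**Step 2: from 45 to 14 per group.** Number remaining = number randomised × (1 − loss).
- 45 × 0.8 = 36, and 36 / 3 = 12 per arm.
- In reverse, 36 / 0.8 = 45 exactly, so 45 is the correct inflation of 12 per arm.
- 14 per arm is 42 in total, a loss of 1 − 42/45 = 6.7%.
- Keeping 42 after 20% loss needs 42 / 0.8 = 52.5, so 53 randomised (54 with equal arms).
- The shortfall against the number behind the quoted power is (42 − 36) / 42 = 14%.

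**Step 3: does the power claim depend on 12 versus 14?** The plan gives no SD or correlation, so the values below are assumptions. Method: two-sided t-test at alpha 0.05 using the noncentral t distribution, with noncentrality 8 / [SD × √(1/n₁ + 1/n₂)]. Baseline adjustment multiplies the SD by √(1 − r²) and costs one degree of freedom.

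Example, SD 6 with 12 per arm, unadjusted: 8 / (6 × √(2/12)) = 3.27 on 22 degrees of freedom, giving 88%.

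| Comparison | Assumed SD 6 | Assumed SD 7 |
|---|---|---|
| 14 v 14, unadjusted | 92% | 83% |
| 12 v 12, unadjusted | 88% | 76% |
| 14 v 14, baseline-adjusted, r = 0.5 | 97% | 92% |
| 12 v 12, baseline-adjusted, r = 0.5 | 95% | 87% |
| 24 v 12 (both CBT-I arms pooled v waitlist), unadjusted | 96% | 88% |

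The largest SD that still gives 90% power is 5.8 at 12 per arm and 6.3 at 14 per arm unadjusted. With r = 0.5 it is 6.65 and 7.24. Between each pair of limits the claim is true at 14 per arm and false at 12; below the lower limit it holds at both.

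**The case against.** **This is a pilot, and 20% is only a potential rate.** The sponsor's earlier pilot study lost nobody, so 14 of 15 might be retained. That is fair as a forecast. But 20% is the allowance the plan chose and says it used to reach 45, and 14 per arm does not follow from it. The plan also tests efficacy hypotheses and claims power for them, so the figures need to agree.

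**Intent-to-treat keeps everyone in.** The plan describes no imputation, and a woman lost before T2 contributes no T2 score. The expected number with T2 data remains 36.

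**Two women per arm is a small difference, and nothing in the trial's conduct changes.** This stands. Enrolment and allocation are consistent throughout, and in many plausible settings power stays above 90% at 12 per arm. It is the reason for treating this as a correction to the justification and not as a flaw in the design.

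**Stronger readings that the documents do not support.**
- A reader might infer that the claim of more than 90% power is false or that the trial is underpowered. Neither follows: the answer turns on an SD and a correlation that the plan does not give.
- A reader might infer that 18 patients for 95% power is impossible, since an unadjusted two-sided t-test at d = 0.8 needs 42 per group. But the plan names a repeated-measures model. With f = d/2 = 0.4, three groups, two time points and a correlation of 0.7, a total of 18 does give about 95%. Those choices are unstated, which makes the figure impossible to reproduce but does not refute it.
- A reader might infer that 54 must be randomised. That follows only if 14 per arm was the true requirement. If 18 was a total, 36 completers already exceed it.

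**Conclusion.** The section is wrong as written on two counts, and neither needs an assumption. Adding 20% attrition to 18 gives 23, not 14. Taking 20% from 45 leaves 36 (12 per arm), not 42 (14 per arm). No transposition or rounding makes 18, 14, 45 and 20% agree.

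The consequence is limited. The quoted power refers to 14% more completers than the plan's allowance leaves. For 8 ISI points the cost is about 2 to 7 percentage points of power over the assumed SDs of 6 and 7, with or without baseline adjustment at r = 0.5. Whether that takes power below 90% cannot be settled from the documents. This should be fixed, but it does not by itself call the sample size into question.

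**What to change.** Keep N = 45 and revise the Sample Size Power Calculation section as follows.

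1. Reconcile 18 and 14: say which is the number required and which the number recruited, and whether each is per arm or total.
2. Replace the statement that 45 allows 14 per group with: 45 randomised, 15 per arm; with 20% attrition, 12 per arm (36 in total) are expected at T2.
3. Restate the power for 8 ISI points at 12 per arm, or at 24 v 12 if the CBT-I arms are to be pooled, giving the assumed SD and correlation.
4. If the required number proves to be 14 or 18 per arm, say that 45 does not meet it after 20% loss, and report the power that 12 per arm does provide in place of the 95% or the above-90% figure.

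The cost is revised wording and one recalculation, with no additional participants. The downside is that the stated power may become less favourable.
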